# Manufacturer

#### **Storage conditions**

At temperature below 25 °C. Keep out of reach of children.

Shelf life

S. SANDOZ Protocol No. TE 004 ANG LOZ

3 years. The drug should not be used after the expiry date.

# 2.2 Summary of preclinical and clinical results significant for this trial

Angal, a drug proposed for the state registration, contains two components; therefore, this section presents a summary of preclinical and clinical aspects of efficacy and safety of those components.

# 2.2.1 Preclinical results summary

# 2.2.1.1 Chlorhexidine (chlorhexidine dihydrochloride)

Chlorhexidine is a commonly used disinfectant and topical antiseptic agent. In vitro tests confirmed the value of chlorhexidine in the treatment of upper respiratory tract infections such as pharyngitis. It exerts bactericidal effects against the pathogenic bacteria in the upper respiratory tract infections. Chlorhexidine also shows some antiviral activity in relation to influenza A virus (H1N1).

Chlorhexidine is virtually not absorbed when administered topically. Small amounts are detected in the urine of laboratory animals. LD50 varies from 21 mg/kg (rats, i.v.) to 5,000 mg/kg (rats, oral). Subchronic toxicity trials showed minimal dermal irritation (erythema, edema, desquamation and/or fissuring) at the lowest dose tested.

Tests at all doses showed no malformations or developmental toxicity. Mutagenic effects were not observed in two mammalian in vivo mutagenesis trials evaluating chlorhexidine gluconate. Long-term toxicity trials in rats showed no carcinogenic effects of chlorhexidine (5; 6; 7; 8; 9; 10).

# 2.2.1.2 Lidocaine (lidocaine hydrochloride)

Lidocaine hydrochloride is a peripheral local anesthetic of the amide type. Lidocaine administered i.v. is used as an antiarrhythmic drug. Lidocaine, like other local anesthetics, blocks conduction of nerve endings impulses in a reversible way by interfering with processes fundamental to generation of nerve action potential, namely, large transient increase in permeability of membrane to sodium ions that is produced by slight depolarization of membrane.

From observations in rabbits administered lidocaine HCl i.v. and portally, a first pass hepatic elimination of approximately 30% could be calculated. The fraction of rectal venous drainage bypassing the portal circulation and thus hepatic metabolism is about 40%. In the rabbit, the hepatic first pass effect for lidocaine can be avoided by administering the compound via the rectum.

Intrinsic clearance of lidocaine was consistently reduced in the dog after repeated administration. LD50 varies from 19.5 mg/kg (mouse, i.v.) to 317 mg/kg (rat, oral). Lidocaine showed neurotoxicity to sensory neurons, resulting from a direct action on sensory neurons, and that a lidocaine-induced increase in intracellular Ca2+ is a mechanism of lidocaine-induced neuronal toxicity. Lidocaine is less cardiotoxic than bupivacaine. Observed neurotoxic effects after intrathecal infusion were dose-dependent. No significant effects were observed in offspring of Sprague Dawley rats administered lidocaine. Lidocaine did not show any mutagenicity. Lidocaine effectively inhibited the invasive ability of human cancer cells at concentrations used in surgical operations (11; 12; 13; 14).

For these reasons, the lozenges containing chlorhexidine hydrochloride (5 mg) / lidocaine hydrochloride (1 mg) are considered to be fully satisfactory for introduction to the market in terms of safety and efficacy. The information presented confirms the suitability of the product when used as recommended.

#### 2.2.2 Clinical results summary

The results of a randomized, double-blind, placebo-controlled, phase III trial with a lemon-flavored lozenge formulation (Medica®) containing a combination of 5 mg chlorhexidine dihydrochloride with 1 mg lidocaine hydrochloride demonstrated higher efficacy than placebo regarding several measured parameters, which exhibited significant improvement from the stationary phase (sore throat at 120 min) through to the follow-up visit at Day 4 (sore throat and erythema). This combination was thus shown to provide symptomatic relief of sore throat as well as reducing signs of inflammation such as erythema. The combination lozenge was very well tolerated. In a double blind, placebo-controlled trial conducted by Schapowal et al., the use of a spray containing chlorhexidine 1% and lidocaine 2% demonstrated a 60% response on Day 3 of the therapy associated with a very good tolerability in patients with an acute tonsillopharyngitis (15).

The use of topical lidocaine forms (pastilles and spray) at much bigger strength than that of Angal was not associated with any toxic effects while a significant clinical effect was shown (16).

Although the overall volume of clinical evidence in support of the proposed indication is very limited and the available data set has not resulted from a systematic investigation of the properties of the product, this type of preparations has been used widely for several decades. The use of the drug at recommended doses for the approved indications is safe; the drug is registered in the EU; no SAEs were reported, while AEs and precautions for use in special

populations are well known and described in Section 2.1.1. Therefore, the repeated toxicological, pharmacological, or clinical trials for determination of the main features of the active substances are not justified, while a benefit/risk ratio is favorable to recommend conduction of a clinical trial of Angal in patients with acute viral pharyngitis.

# 2.3 Brief description of known and potential risks for the trial subjects (if any)

Preclinical and clinical trials of the study drugs components showed a favorable safety profile and good tolerability of Angal and ANTI-ANGIN® FORMULA. A list of known side effects of those drugs is presented in Section 2.2.1.

Venous blood will be collected during the trial, approximately 12 ml (1 tablespoonful) on Day 0 and Day 4, i.e., the total amount of blood taken for analysis will not exceed 30 ml for 5 days. Those volume and rate of a blood loss are clinically insignificant for an adult. Venipuncture may potentially cause a bruise or hematoma, as well as phlebitis or thrombophlebitis at the injection site. The trial site personnel will make every possible effort to minimize the risks for the patients associated with the trial therapy and procedures. In case of AEs or other health issues, the patient will be provided with the appropriate medical care.

The benefit from the trial is associated with the laboratory and instrumental investigations, therapy under supervision of a highly qualified doctors with the study drugs free of charge for the trial participants.

# 2.4 Description and rationale for the route of administration, dosages, dosing regimens, and duration of treatment

The study drugs will be prescribed according to relevant Prescribing Information: a Prescribing Information draft for Angal and a current Prescribing Information for ANTI-ANGIN® FORMULA registered in Russia. Angal will be used in the following way: 1 lozenge with a not less than 2-hour interval, till full dissolution in the mouth, up to 6–10 times per day, for 4 days or until full recovery (whichever occurs first during 4 days of therapy). ANTI-ANGIN® FORMULA will be used in the following way: 1 lozenge with a not less than 2-hour interval, up to 6 lozenges per day, for 5 days or until full recovery (total TSS  $\leq$  2) (whichever occurs first during 5 days of therapy).

S. SANDOZ

# 2.5 Legal basis

This is a protocol of clinical trial planned to be conducted in accordance with principles of the Declaration of Helsinki, World Medical Association (adopted at the 18th Assembly of the World Medical Association in Helsinki in June 1964, the latest revision adopted by the 64th Assembly in Fortaleza in October 2013), the triangular agreement on Good Clinical Practice (ICH GCP), and applicable laws of the Russian Federation:

- Federal Law *On Circulation of Medicines* No. 61-FZ of April 12, 2010 (current version No. 350-FZ of July 3, 2016).
- Federal Law *On Personal Data* No. 152-FZ of July 27, 2006 (current version of July 21, 2014 as amended as of September 1, 2015).
- The National RF Standard GOST R52379-2005, *Good Clinical Practice*.
- Government Decree of the Russian Federation No. 714 of September 13, 2010 (the last version of October 15, 2014), *Rules for compulsory insurance of the life and health of a patient involved in clinical trials of a drug.*
- Order of the Ministry of Health of the Russian Federation *On Approval of the Provision on the Ethics Council* No. 986n of November 29, 2012.
- Order of the Ministry of Health of the Russian Federation *On Approval of the Good Clinical Practice Rules* No. 200n of April 1, 2016.

# 2.6 Description of the trial population

Men and women at the age of 18 to 45 years old, inclusively, with acute, uncomplicated, inflammatory and infectious conditions of the pharynx associated with a sore throat, with manifestation of the first signs not more than 48 hours before the inclusion, with a total TSS  $\geq$  5, who signed the Informed Consent Form and comply with the inclusion criteria (see Section 5.1) and none of the non-inclusion criteria (see Section 5.2).

#### Confidential

# **3** Trial objectives and goals

# 3.1 Trial objective

This trial has been designed to evaluate the non-inferior therapeutic efficacy and safety of the study drug Angal, lozenges [menthol], 1 mg + 5 mg (Sandoz d.d., Slovenia), comparing to ANTI-ANGIN® FORMULA, lozenges, 0.2 mg + 2 mg + 50 mg (OOO Valeant, Russia), in treatment of patients with uncomplicated acute infectious and inflammatory diseases of the pharynx accompanied by a sore throat.

# 3.2 Trial goals

#### **Primary goal:**

• Assessment of the non-inferior therapeutic efficacy of Angal, lozenges [menthol], 1 mg + 5 mg (Sandoz d.d., Slovenia)—administration of 1 lozenge with a not less than 2-hour interval, up to 6–10 times per day, for 4 days or until full recovery (whichever occurs first during 4 days of therapy), compared to ANTI-ANGIN® FORMULA, lozenges 0.2 mg + 2 mg + 50 mg (OOO Valeant, Russia)— administration of 1 lozenge with a not less than 2-hour interval, up to 6 lozenges per day, for 5 days or until full recovery (whichever occurs first during 5 days of therapy) in the treatment of patients with uncomplicated acute infectious and inflammatory diseases of the pharynx accompanied by a sore throat.

#### Secondary goals:

- Assessment of safety of Angal, lozenges [menthol], 1 mg + 5 mg (Sandoz d.d., Slovenia) administration of 1 lozenge with a not less than 2-hour interval, up to 6–10 times per day, for 4 days or until full recovery (whichever occurs first during 4 days of therapy), compared to ANTI-ANGIN® FORMULA, lozenges, 0.2 mg + 2 mg + 50 mg (OOO Valeant, Russia)—administration of 1 lozenge with a not less than 2-hour interval, up to 6 lozenges per day, for 5 days or until full recovery (whichever occurs first during 5 days of therapy) in the treatment of patients with uncomplicated acute Infectious and inflammatory diseases of the pharynx accompanied by a sore throat.
- Evaluation of adverse events (AEs) in the trial arms.
- The AEs rate comparison between the trial arms.

S. SANDOZ

# 4 Trial design

# 4.1 General and additional tested parameters

#### 4.1.1 Efficacy parameters

# 4.1.1.1. The main efficacy endpoint

The primary outcome measure was the percentage of patients without sore throat after 3 days of therapy on Day 4, as evaluated by the Investigator according to the Tonsillopharyngitis Severity Score (TSS), in both Angal and ANTI-ANGIN® FORMULA arms.

# 4.1.1.2 Additional efficacy endpoints

The secondary outcome measures in the both therapy groups to compare the therapeutic efficacy of the study drug and comparator drug were:

- The frequency of ≥50% total score reduction according to the TSS questionnaire completed by the Investigator as compared to the baseline in both Angal and ANTI-ANGIN® FORMULA groups at Visit 2 (Day 4).
- Total score reduction according to the TSS questionnaire, as well as a reduction in the symptoms (sore throat, difficulty in swallowing, salivation, erythema, and fever) after a 3-day therapy, at Visit 2 (Day 4), as compared to the baseline total score.
- A period of time required for disease symptoms relief, determined according to the patient's diary (subjective patient's evaluation), but no more than 5 days during the trial—for patients who have achieved the corresponding outcome.
- A proportion (%) of patients who fully recovered by Day 4 in Group A and by Day 5 in Group B (the outcome of a disease according to the objective evaluation by the Investigator, the total score according to the TSS questionnaire ≤2).
- A change in the sore throat intensity by 100 mm VAS (visual analogue scale filled in by the patient) at the beginning, after 3 days of therapy, and at the end of treatment in both groups.

# 4.1.2. Safety parameters

The following parameters will be taken into account for the safety evaluation:

- AEs and/or SAEs rates per trial arms;
- Global tolerance evaluation during the trial by the Investigator and patient;
- Vital signs (heart rate, blood pressure, body temperature, breathing rate);
- ECG parameters;
- Laboratory results.

The AEs will be described according to the scheme given below:

# Confidential

- ae description;
- ae severity;
- ae duration;
- Relation to the study drug;
- Outcome.

All AEs will be coded according to MedDRA terms.

# 4.2 Description of the trial design

# 4.2.1 Trial type

Prospective, multicenter, open, randomized, comparative, clinical trial in 2 parallel groups.

# 4.2.2 Trial design flowchart

# 4.2.3 Trial procedures

# 4.2.3.1 Trial procedures in a table form

#### Table 1. Visit schedule

Trial period	Screening/Randomization/Therapy initiation	Treatment		Further follow-up 	Unscheduled visits
Visits	Visit 1	Visit 2  Visit 3 		Visit 4	
Day after initiation of therapy	Day 1	Day 4 Day 5		Day 6/7	
Trial procedures					
Signing of the Informed Consent Form	•				
Demographic data (date of birth, sex, age)	•				
Measurement of weight and height	•				
Medical history	•				
Collection of complaints, actualization of anamnesis	•	•	•		•
Records on the concomitant therapy	•	•	•		•
Evaluation of the throat pain intensity according to VAS by a patient	•	•	•		
Fill-in of TSS questionnaire 	•	•	•		•
Physical examination (including topical examination)	•	•	•		•
Measurement of vital signs 	•	• *	•		•
Hematology 	•	• *	•		
Biochemistry 	•	• *	•		
Urine pregnancy test 	•				
12-lead ECG	•	• *	•		
Evaluation of inclusion/non-inclusion criteria	•				

<sup>1 A follow up visit will be held in the form of a phone contact with the patient to reveal the possible AEs.

<sup>2 In case of premature discontinuation, the follow-up procedures are the same as those at Visit 2.

<sup>3 Only for the Group B patients who did not meet the recovery criteria (total  $TSS \le 2$ ) at Visit 2 (Day 4) and continued the therapy.

<sup>4 Fill-in of TSS questionnaire by the Investigator (scores for every question should be summarized to obtain a total TSS score).

<sup>5 Systolic blood pressure (mm Hg), diastolic blood pressure (mm Hg), breathing rate (per minute), pulse rate (beats per minute), axillary body temperature (°C).

<sup>6 Hb, RBC, WBC with differential, ESR—at the trial site laboratory.

<sup>7 Total protein, AST, ALT, total bilirubin.

<sup>8 For women with the preserved childbearing potential only.

Trial period	Screening/rand omization/ther apy initiation	Treatment		Further follow-up 	Unscheduled visits
Visits	Visit 1	Visit 2 	Visit 3 	Visit 4	
Day after initiation of therapy	Day 1	Day 4	Day 5	Day 6/7	
Trial procedures					
Randomization	•				
Dispensing of the study drugs	•				
Dispensing of the patient's diaries	•				
Return of the unused study drugs		• *	•		
Return of the patient's diaries		• *	•		
Evaluation of adverse events (including based on results of the throat and pharynx examination during the trial site visits)	•	•	•	•	•
Evaluation of exclusion criteria		•	•		•
Global evaluation of therapy tolerability by the patient and the physician		• *	•		•
Compliance evaluation (diary completion, administration of the study drugs)		•	•		•

Notes:

\* Only for Group A patients and those Group B patients who achieved the recovery criteria (total TSS score  $\leq 2$ ).

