# 4.2.4.2 Efficacy evaluation visit (Visit 2, Day 4)

Visit 2 is conducted on Day 4; the patient must visit the trial site in the fasted state and bring the filled-in diary and unused drug.

If Group B patients (ANTI-ANGIN® FORMULA) did not meet recovery criteria (total  $TSS \le 2$ ) at Visit 2 (Day 4), they will require continuation of the therapy, and some procedures for those patients will be transferred for the next day (Visit 3, Day 5), see below. The patients will keep their diaries and the unused drugs.

Visit 2 procedures for the both groups:

- Collection of complaints, actualization of anamnesis;
- Records on the concomitant therapy;
- Physical examination (including oropharynx);
- Measurement of the main vital signs;
- Evaluation of adverse events (including based on results of the throat and pharynx examination);
- Evaluation of exclusion criteria;
- Compliance evaluation (diary completion, administration of the study drugs).

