# Visit 2 procedures for Group A patients (Angal) and Group B (ANTI-ANGIN® FORMULA) who achieved recovery criteria (total TSS $\leq$ 2):

- Hematology;
- Biochemistry;
- 12-lead ECG;
- Global evaluation of treatment tolerability during the trial by the physician and the patient;
- Return of the unused study drug;
- Return of the patient's diary;

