# 4.1.5 Analysis of laboratory and functional tests results

A between group comparison of the vital signs changes (systolic blood pressure, diastolic blood pressure, breathing rate, heart rate, body temperature) revealed at every visit (Visits 1, 2, 3) as well as laboratory results and ECG changes incidence obtained at Visit 1 and Visits 2–3 is envisaged. In addition, significance of the changes will be evaluated for all repeatedly measured parameters.

The following laboratory parameters will be reviewed:

- Hematology
  - o Hemoglobin
  - o RBC
  - o ESR
  - o WBC
  - o Neutrophils
    - Juvenile
    - Stab
    - Segmented
  - o Eosinophils
  - o Basophils
  - o Monocytes
  - o Lymphocytes
- Biochemistry
  - o Total protein
  - o AST
  - o ALT
  - o Total bilirubin

ANOVA methods will be used to reveal a simultaneous influence of a group and time factors on the quantitative parameters.

The cross tables analysis will be used to reveal a correlation between the qualitative parameters (chi-squared test).

For the quantitative parameters, a comparison will be made by Student's t-test for the independent samples (in case of confirmation of hypothesis on normal variables distribution) or Mann–Whitney test (in case of rejection of hypothesis on normal variables distribution); for the qualitative parameters—using Fisher's exact test.

To evaluate significance of the intragroup changes during the trial for repeatedly measured parameters, the paired Student's t-test (in case of confirmation of hypothesis on normal variables distribution) or paired Wilcoxon signed-rank test (in case of rejection of hypothesis on normal variables distribution) will be used; for the qualitative parameters McNemar's test will be used.

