# Table 20. Global evaluation of treatment tolerability (Visits 2, 3)

# Table 21. Registered adverse events occured after initiation of the trial therapy

	Mile	d AEs	Moder	ate AEs	Sever	re AEs	To	otal	Total
Description	Serious	Non-serious	Serious	Non-serious	Serious	Non-serious	Serious	Non-serious	Serious +
	Schous	Non-serious	Schous	i von-serious	Serious	Inoll-serious	Schous	Non-serious	non-serious
				Organ syst	tem				
	Organ system								

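### Table 1 limits Visit 2 vital signs in Group B to recovered patients, against the protocol and SAP text, and the SAP does not rule out by-visit safety tests that select one arm on recovery

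*Protocol*

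**What the plan says.** **Table 1 (protocol 4.2.3.1).** In the Visit 2 column, asterisks mark vital signs, hematology, biochemistry, ECG, return of drug and diary, and global tolerability. The note reads "Only for Group A patients and those Group B patients who achieved the recovery criteria", recovery being total TSS ≤ 2. The TSS, VAS and exclusion-criteria rows carry no asterisk. A footnote limits Visit 3 to Group B patients who had not recovered at Visit 2.

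**Visit text.** Protocol 4.2.4.2 has a list headed "Visit 2 procedures for the both groups" that includes "Measurement of the main vital signs" with no recovery condition. The synopsis and SAP 3.8.2 do the same. A second list, for Group A and recovered Group B only, contains hematology, biochemistry, ECG and "Global evaluation of treatment tolerability during the trial by the physician and the patient".

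**Analysis.**
- SAP 4.1.5 compares vital-sign changes between groups as "revealed at every visit (Visits 1, 2, 3"), and laboratory and ECG results between Visit 1 and Visits 2–3.
- Protocol 9.1.4 adds a two-way ANOVA with group and visit as factors, and a chi-square test for tolerability.
- The caption of SAP Table 20 is "Global evaluation of treatment tolerability (Visits 2, 3"), and the template has a p row.
- Protocol 9.5 and SAP 3.6 analyze everything except the primary endpoint on available data, without replacement.

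**The concern.** Recovery is a post-randomization outcome. If one arm is measured whole and the other only where the patient has recovered, the two sets are no longer comparable by randomization. Pulse, blood pressure and tolerability ratings may depend on whether the patient is still ill, so a difference could appear at Visit 2 between two equally safe products. If patients who are still ill rate tolerability lower, the artefact would run against Angal. At Visit 3 there is no Group A patient to compare, so a between-group test there is impossible and the group-by-visit ANOVA has an empty cell. What is at stake is the secondary safety and tolerability comparison.

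**Working it through.** The plan gives no figure to reproduce here, so the check has two parts.

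**1. Passages side by side**

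| Visit 2 item | Table 1 | Visit 2 text (protocol 4.2.4.2, SAP 3.8.2) |
|---|---|---|
| Vital signs | all of A, recovered B | both groups, everyone |
| Tolerability, hematology, biochemistry, ECG | all of A, recovered B | all of A, recovered B |
| Exclusion criteria | everyone | both groups, everyone |
| TSS | everyone | not itemized |

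The vital-signs asterisk also conflicts with Table 1 itself. Axillary temperature is one of the vital signs (footnote to the row "Measurement of vital signs") and one of the five TSS items, so it must be known before TSS ≤ 2 can be judged. A temperature above 37.5 °C also appears in the first exclusion criterion (protocol 5.3.1), and exclusion criteria are checked at Visit 2 in everyone.

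**2. Possible size if the restricted set is tested**

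Inputs:
- 140 randomized per arm (protocol 9.2), no dropout.
- Two-sided alpha 0.05 for non-primary comparisons (protocol 9.3).
- r, the share of patients with TSS ≤ 2 on Day 4: not in the documents. The 63% expected without sore throat on the comparator (protocol 9.2) is only a proxy, so r is varied from 40% to 90%.
- No true drug effect, and the same r in both arms.
- The gap between recovered and non-recovered patients is assumed. Good or excellent tolerability: 95% versus 80%, or 95% versus 90%. A continuous vital sign: 0.5 or 0.2 of the within-stratum SD.

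Formulas:
- Group B measured = 140r.
- Tolerability: pA = r·a + (1−r)·b and pB = a, so the spurious gap is d = (1−r)(a−b). Rejection rate = 1 − Φ((1.96·se0 − d)/se) + Φ((−1.96·se0 − d)/se), with se0 the pooled and se the unpooled standard error.
- Vital sign: bias = (1−r)·δ in SD units; se = √[(1 + r(1−r)δ²)/140 + 1/nB].

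At r = 0.63, 95% versus 80%:
- nB = 88, with 52 omitted.
- pA = 0.63×0.95 + 0.37×0.80 = 0.8945, so d = 0.0555.
- se0 = 0.0378, se = 0.0348.
- (1.96×0.0378 − 0.0555)/0.0348 ≈ 0.53, which gives a rejection rate of about 30%.

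At r = 0.63, δ = 0.5:
- bias = 0.37×0.5 = 0.185, se = 0.1376, ratio 1.34.
- Rejection rate about 27%.

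| r | B measured / omitted | Tolerability 95 v 80: gap, rejection | 95 v 90: gap, rejection | 0.5 SD: bias, rejection | 0.2 SD: bias, rejection |
|---|---|---|---|---|---|
| 40% | 56 / 84 | 9.0 points, 42% | 3.0, 9% | 0.30, 47% | 0.12, 12% |
| 63% | 88 / 52 | 5.55 points, 30% | 1.85, 8% | 0.185, 27% | 0.074, 8% |
| 90% | 126 / 14 | 1.5 points, 8% | 0.5, 5% | 0.05, 7% | 0.02, 5% |

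With everyone measured at Visit 2, or one end-of-treatment value per patient, the sets are 140 and 140. The selection bias is then zero and the rate returns to 5%, provided that Day 4 versus Day 5 timing does not itself shift the value.

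**The case against.** A reader might infer that the Visit 2 safety comparison is confounded as planned. The documents do not support that, for four reasons.

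- **Vital signs.** The synopsis, protocol 4.2.4.2 and SAP 3.8.2 all put them in the list for both groups. One asterisk against three texts looks like a slip, and bias arises only if sites follow the asterisk. Temperature is the vital sign least likely to be missing, since the Visit 2 TSS needs it in everyone.
- **Tolerability.** Protocol 4.2.3.2.5 and SAP 2.3 record the rating at Visit 2 or Visit 3, which is one rating per patient. Protocol 9.1.4 attaches a by-visit breakdown to laboratory, vital-sign and ECG incidences but not to tolerability. The SAP Table 20 template has no visit columns. A test on one pooled rating is a natural reading.
- **Size.** In the active arm of the cited placebo-controlled trial, 62.5% + 26.0% = 88.5% had absent or mild sore throat on Day 4 (protocol 9.2). That is a single TSS item, but a small unrecovered share is plausible.
- **Consequence.** SAP Section 4 rests the non-inferiority conclusion on the primary parameter alone and treats safety variables as being of research interest.

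All four stand as limits. They do not remove the contradiction in the operational schedule, and they do not supply the missing pooling rule. SAP 4.1.5 does name all three visits for vital signs, and its range of Visits 2–3 for laboratory and ECG may mean pooling but does not say so.

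**Conclusion.** The contradiction on vital signs is certain and rests on no assumption. The selection is conditional: for vital signs it depends on sites following Table 1, and for tolerability, laboratory and ECG it depends on the tests being run by visit. Under those conditions the comparison is selected on recovery in one arm only. Its size cannot be fixed from the documents. With the assumed inputs above it runs from negligible (rejection near 5%) to a false-positive rate of 30% or more, and no single value should be quoted as the expected bias. It also cannot be claimed that Angal would look worse tolerated, because that direction rests on an assumed link between illness and rating. The primary endpoint is unaffected, since TSS at Visit 2 is unstarred. The correction should be made before analysis, but it does not threaten the main conclusion.

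**What to change.** 1. Reconcile the vital-signs row of Table 1 with protocol 4.2.4.2, the synopsis and SAP 3.8.2, so that both arms are measured alike at Visit 2.
2. In SAP Table 20 and for the tolerability chi-square test, state that the between-arm test uses one end-of-treatment rating per patient (Visit 2, or Visit 3 where held), with no p-value by visit.
3. Apply the same rule to the starred laboratory and ECG comparisons in SAP 4.1.5, and say what Visits 2–3 means there.

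The cost is one symbol in Table 1 and a few lines in the SAP. There is no new visit, and no procedure that the Visit 2 text does not already list. The remaining drawback is timing: non-recovered Group B patients contribute a Day 5 value and all others a Day 4 value, which should be noted beside the tables.
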